9.3 VARIABLES

Detailed definitions of variables that will be derived for statistical analyses and summaries will be included in the Statistical Analysis Plan (SAP). Variables and their description are shown on (see [Appendix Table 1](#)).

9.3.1 Exposures

The exposure measures are based on the prescription of LAMA or fixed dose combination of ICS/LABA. Using the medication possession ratio (MPR), to describe adherence, the case of overall

mean MPR $\geq 80\%$ defined as good adherence. Therefore, usually one inhaler is used per month, this study includes patients who have been prescribed total more than 10 inhalers per 12 months (1 year).

9.3.2 Outcomes

9.3.2.1 Primary outcomes

Primary endpoint

- Recorded pneumonia based on 1)ICD-10 code (J12.x-J18.x, J69.0, J84.9, B96.0, J85.1) AND 2) CPT code of chest x-ray(71045-71048) or chest CT(71250,71260,71270,G0297) AND 3) prescription of antibiotics for pneumonia in Korean Guideline) incidence rate per year
- Frequency rate of COPD exacerbation per year
 - Moderate exacerbation: recorded as when COPD patients visited outpatient clinics with an ICD-10 code of COPD and systemic steroid medication and/or antibiotics were prescribed (within the first year after initial prescription of inhalers)
 - Severe exacerbation: when COPD patients visited the emergency room or were admitted to hospital with an ICD-10 code of COPD(*due to COPD worsening*) and were prescribed systemic steroid medication and/or antibiotics (within the first year after initial prescription of inhalers)
- Time to start triple combination therapy ICS/LABA/LAMA)
 - Time to add LAMA in patients with using ICS/LABA or, time to add ICS/LABA in patients with using LAMA before.

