9.2 SETTING

The study will be conducted in a general practice setting, Korea National Health Insurance claim data & mortality data from the Bureau of Statistics, which includes computerized medical records of more than half million patients in South Korea. The maximal observation period will be from Jan 2005 to Apr 2016.

- Inclusion criteria
 - Diagnosed with COPD [**based on ICD-10 code(J43.x-44.x except J430), as the primary or within the fourth secondary diagnosis and initiated LAMA or ICS/LABA more than twice a year from Jan 1, 2005 to Apr 30 2016**].
 - Age >55 years old as of 2005 when enroll started
- Exclusion criteria
 - Prescription history with any long acting bronchodilator for maintenance therapy (the patient should be inhaler naïve) from 2002 to 2005.
 - Prescription history with ipratropium bromide
 - Prescription history with Leukotriene receptor antagonist(LTRA) or ICS
 - Prescription history of LABA/LAMA FDC
 - Patients with lung cancer, IPF, ILD or lung transplantation at the time of COPD diagnosis

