9.6 DATA MANAGEMENT

We will collect the data from the medical insurance claims from the Korean National Health Insurance (NHI) claims database, which will be provided for research purposes by the Korean NHIC with strict confidentiality guidelines All analyses were performed with SAS and R .

Data for this study will be obtained via the following sources:

- Eligibility DB
 - Sociodemo-graphics variables : sex, age, residential area, insurance type (the employee insured, the self-employed insured, dependants, medical aid), monthly contributions, occupation
 - Vital statistics : dates of birth and death, cause of death (ICD-10 codes)
- Health care utilization DB
 - Diagnosis : International Classification of Disease-10 codes (main disease code, sub disease code)
 - Utilization and cost : date of visit, types of medical institutions (clinics/hospitals/tertiary hospitals/public health centres), types of visit (inpatient/outpatient/emergency/intensive care), length of stay, medical cost (insurer/patient), et al.
 - Health care procedures and medications : Operation and procedure codes, medication history (generic name code, dose, duration of prescription), material codes, et al.

Data is extracted from the NHIS and stored on a secured, shared server for statistical analyses. The original data will be stored in its own, read-only directory to protect the integrity of the extracted data. After obtaining an approval from the NHIS, data analysts can access the data and conduct analysis in a secured computer. NHIS's policy strictly forbids exportation of the original data, however, results obtained from statistical analyses can be exported after an internal review.

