Health care utilization outcomes will be analyzed separately in each treatment group. Analyses will be conducted for 1)total health care expenditure 2)COPD-related utilization and cost for all of the medical resource utilization and costs during the follow-up period. For outpatient services, analyses were confined to visits with the ICD-10 code of COPD (J43.x–J44.x, except J430) with the prescription of COPD-related medication. For inpatient services, analyses were confined to admission with ICD-10 code of COPD or COPD-related disease (pneumonia: J12.x–J17.x, pulmonary thromboembolism: I26, I26.0, and I26.9; dyspnea: R06.0; or acute respiratory distress syndrome: J80) with the prescription of COPD-related medication. Medical costs per person per year will be reported overall and separately based on type of service: inpatient healthcare visits, outpatient healthcare visits, and pharmacy dispensations. This involves calculating the average cost among members who are alive in the beginning of a month.

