ANNEX 3. ADDITIONAL INFORMATION

Appendix Table 1. List of variables in the NHIS database

DB (number of variables)	Variable name	Details
The eligibility of the insured DB	STND_Y	Standard year for the eligibility of the insured
	PERSON_ID	Personal identification number is replaced by serial number
	SEX	Sex
	AGE_GROUP	Age group at time of diagnosed
	DTH_YM	Year and month of death
	DTH_CODE1	Level 1 (detailed) cause of death
	DTH_CODE2	Level 2 cause of death
	SIDO	Province of residence
	SGG	District of residence
	CTRB_PT_TYPE_CD	Percentile group of income level
The medical treatment DB (called Table 20) [electronic bill of medical treatment]	PERSON_ID	Personal identification number is replaced by serial number
	KEY_SEQ	Key sequence number of claim
	YKIHO_ID	Medical care institution identification number
	RECU_FR_DT	The first day of receiving treatment
	FORM_CD	Form of claimed bill
	DSBJT_CD	Medical subject code
	MAIN_SICK	Main disease code
	SUB_SICK	Sub disease code
	IN_PAT_CORS_TYPE	Route through hospitalization
	OFFC_INJ_TYPE	Type of injuries incurred while on duty

DB (number of variables)	Variable name	Details
	RECN	Days of receiving medical care
	VSCN	Days of visit hospitals or inpatient
	FST_IN_PAT_DT	First date of inpatient
	DMD_TRAMT	Amount of medical expenses based on claims
	DMD_SBRDN_AMT	Expenses paid by beneficiary based on claims
	DMD_JBRDN_AMT	Expenses paid by insurer based on claims
	DMD_CT_TOT_AMT	Total amount for CT based on claims
	DMD_MRI_TOT_AMT	Total amount for MRI based on claims
	EDEC_ADD_RT	Extra rate applied based on claims reviewed
	EDEC_TRAMT	Amount of medical expenses based on claims reviewed
	EDEC_SBRDN_AMT	Amount of expenses paid by beneficiary based on claims reviewed
	EDEC_JBRDN_AMT	Amount of expenses paid by insurer based on claims reviewed
	EDEC_CT_TOT_AMT	Total amount for CT based on claims reviewed
	EDEC_MRI_TOT_AMT	Total amount for MRI based on claims reviewed
	DMD_DRG_NO	DRG number of claim
	MPRSC_ISSUE_ADMIN_ID MPRSC_GRANT_NO	Institution identification number which issued prescriptions Prescription identification number (newly added since 2011 database)
	TOT_PRES_DD_CNT	Total days of prescription
	KEY_SEQ	Key sequence number of claim

DB (number of variables)	Variable name	Details
The medical treatment DB (called Table 30) [details of medical treatment bill]	SEQ_NO	Sequence number
	RECU_FR_DT	Date of the first treatment
	CLAUSE_CD	Code for clause
	ITEM_CD	Code for item
	DIV_TYPE_CD	Code for the type of treatment

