	DIV_CD	Code for treatment
	I_II_TYPE	Code for an application of additional rate (Type I or II))
	UN_COST	Amount of unit cost
	AMT	Amount of cost paid
	DD_MQTY_EXEC_FREQ	Amount of daily dose or frequency of medication
The medical treatment DB (called Table 40) [details of disease]	MDCN_EXEC_FREQ	Total days of medication or frequency of medication
	DD_MQTY_FREQ	Amount of single dose
	KEY_SEQ	Key sequence number of claim
	SEQ_NO	Sequence number
	RECU_FR_DT	Date of the first treatment
The medical treatment DB (called Table 60) [details of prescription]	DSBJT_CD	Code for medical examination
	SICK_SYM	Code for disease
	KEY_SEQ	Key sequence number of claim
	SEQ_NO	Sequence number
	RECU_FR_DT	Date of the first treatment
	DIV_TYPE_CD	Code for the type of treatment
	DIV_CD	Code for treatment

DB (number of variables)	Variable name	Details
	GNL_NM_CD	Code for generic medication name
	DD_MQTY_FREQ	Amount of single dose
	DD_EXEC_FREQ	Amount of daily dose
	MDCN_EXEC_FREQ	Total days of medication or frequency of medication
	UN_COST	Amount of unit cost
	AMT	Amount of cost

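### The primary pneumonia definition counts ICD-10 code J84.9, so interstitial lung disease arising during follow-up can be recorded as a primary pneumonia event

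*Combined protocol and SAP*

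**What the plan says.** Section 9.3.2.1 makes recorded pneumonia the first primary endpoint. An event needs a diagnosis code, an imaging code and an antibiotic, joined by AND. The diagnosis step and the start of the imaging step read "ICD-10 code (J12.x-J18.x, J69.0, J84.9, B96.0, J85.1) AND 2) CPT code of chest x-ray(71045-71048". The imaging and antibiotic steps read "CPT code of chest x-ray(71045-71048) or chest CT(71250,71260,71270,G0297) AND 3) prescription of antibiotics for pneumonia in Korean Guideline". The section gives no time window and no same-claim rule linking the three conditions.

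Section 9.2 (and the abstract) lists among the exclusions "Patients with lung cancer, IPF, ILD or lung transplantation at the time of COPD diagnosis". The condition is tied to the date of COPD diagnosis, and nothing visible censors or excludes interstitial disease coded afterwards.

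On where imaging would be found, section 9.6 describes the source as holding "Health care procedures and medications : Operation and procedure codes, medication history". Annex 3 gives the procedure field DIV_CD only as "Code for treatment". Neither place names the coding system for procedures or maps CPT codes to it.

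Section 9.3 leaves detailed variable definitions to the SAP. Section 9.7 says that major changes to primary endpoint definitions would go through a protocol amendment.

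**The concern.** J84.9 is the only code in the diagnosis list that, on its standard meaning, names the condition that section 9.2 screens out at baseline. The other two conditions narrow the problem without closing it. Chest imaging is a plausible part of any work-up for interstitial disease. Antibiotics are common enough in COPD that section 9.3.2.1 itself uses them to define exacerbations. With no window linking the three conditions, an antibiotic given for an exacerbation could complete a pneumonia event that began with an interstitial disease code.

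If such events occur at the same rate in both arms, they carry no information on the effect of inhaled corticosteroid. They dilute the comparison that the study is chiefly built to make, and they do so towards no difference.

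A lesser matter is that the imaging condition is mandatory but is written in CPT codes, with no statement of how these relate to what the database stores. A second analyst could not run the definition from the text alone.

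**Working it through.** The plan gives no pneumonia rate, no target hazard ratio and no share of events coded J84.9. It has no figure to reproduce, and everything numerical below is illustration on stated assumptions.

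**1. Can a J84.9 case reach the endpoint?**

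- At COPD diagnosis: interstitial lung disease leads to exclusion (9.2).
- After COPD diagnosis: no exclusion applies.
- Diagnosis step: met by J84.9 (9.3.2.1).
- Imaging step: met by any listed chest x-ray or chest CT code.
- Antibiotic step: met by a guideline pneumonia antibiotic, with no stated link in time.

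The path is open for interstitial disease that arises during follow-up.

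**2. What would it do to the hazard ratio?**

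Take the hazard ratio (HR) as ICS/LABA relative to LAMA, so that LAMA is the reference arm. Let the reference arm have a true pneumonia rate *a* and a false-positive rate *f*, with *f* the same in both arms. Let q = f/(a + f) be the false-positive share of recorded events in the reference arm. Then

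HR observed = (HR × a + f)/(a + f) = (1 − q) × HR + q.

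Equivalently, the excess over 1 shrinks by the fraction q.

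For a true HR of 1.5 and q = 10%: 0.90 × 1.5 + 0.10 = 1.45.

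For scale, the number of recorded events needed for 80% power at two-sided 5% with 1:1 allocation follows from Schoenfeld's formula, D = 4 × (1.960 + 0.842)² / (ln HR)². The plan sets no power target, and its Cox model is stratified by matched pair, so the counts are only a guide to relative cost.

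| Share q | Observed HR (true 1.5) | Events | Observed HR (true 1.2) | Events |
|---|---|---|---|---|
| 0% | 1.500 | 191 | 1.200 | 945 |
| 1% | 1.495 | 195 | 1.198 | 962 |
| 5% | 1.475 | 208 | 1.190 | 1038 |
| 10% | 1.450 | 228 | 1.180 | 1147 |
| 20% | 1.400 | 278 | 1.160 | 1426 |

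At 1% the effect is negligible. At 10% the events needed rise by about a fifth (228/191 = 1.19; 1147/945 = 1.21). At 20% they rise by about half (278/191 = 1.46; 1426/945 = 1.51).

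**3. Is the imaging step shown to fail?**

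No. Annex 3 is headed "Appendix Table 1. List of variables in the NHIS database". It lists field names with short descriptions, and it shows no ICD-10 or drug code values either. The absence of CPT codes from it is therefore uninformative. What can be said is that the documents do not state the coding system of DIV_CD or a mapping to it.

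**The case against.** The strongest reply is that a broad diagnosis list trades specificity for sensitivity, and that the imaging and antibiotic conditions are there to restore specificity. The baseline exclusion also removes prevalent interstitial disease. This stands in part: it limits the likely share of false positives and argues against a large effect. It does not explain why this code should be in the list.

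It may also be said that definitions are deferred to the SAP. That does not cure a rule which the protocol already states in full, and section 9.7 itself routes major changes to primary endpoint definitions through an amendment. The checklist cites a section 9.7.3 for outcome validity and sensitivity analyses. Its text is not visible and its entry in the contents appears to be redacted, so nothing is inferred from its absence.

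Four stronger readings are tempting, and the documents do not support them:

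- *J84.9 contradicts the exclusion criterion.* It does not. A condition can be excluded at baseline and still be counted later; lung cancer is treated this way, as an exclusion in 9.2 and a secondary outcome in 9.3.2.2.
- *The other pneumonia list shows that J84.9 is wrong.* The utilization text in 9.7.2 uses "pneumonia: J12.x–J17.x, pulmonary thromboembolism" and further conditions to pick out COPD-related admissions. That list also omits J18, J69.0, J85.1 and B96.0, so it says nothing specific about J84.9.
- *The CPT rule will return no events.* This depends on what DIV_CD holds, which the documents do not say; section 9.6 says that procedure codes are available.
- *The endpoint is mis-measured.* No figure in the documents shows that J84.9 events are frequent, so only a risk of misclassification is established.

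**Conclusion.** The point holds as a risk of false-positive primary events. It rests on two things: the standard ICD-10 meaning of J84.9, which comes from outside the documents, and the fact that interstitial lung disease is excluded only at COPD diagnosis. If its occurrence is unrelated to treatment, the bias is towards a hazard ratio of 1. If rates differ between arms, the dilution formula does not apply and the direction is not fixed.

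The size cannot be known from the documents. Over the assumed range of 1% to 20% of reference-arm events, a true hazard ratio of 1.5 would be seen as 1.495 to 1.40, so the effect is small unless J84.9 makes up a sizeable share. The case for acting is that the edit is cheap and makes a primary endpoint more specific, not that serious bias has been shown.

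The unstated imaging-code mapping is missing detail and ranks second.

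**What to change.** 1. Remove J84.9 from the diagnosis list in 9.3.2.1 before outcome data are analysed.
2. Pre-specify a sensitivity analysis that puts J84.9 back, and report the number of events by arm that qualify only through it. This replaces the assumed shares above with an observed one.
3. As a clarification, list the chest x-ray and chest CT codes as they are recorded in DIV_CD, or give a fixed mapping from the CPT codes, also before outcome analysis.

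The cost is a code-list amendment, with the approvals that section 9.8 requires, and one additional analysis run. No new data are needed. The downside is that a few true pneumonias coded only J84.9 leave the primary count; the sensitivity analysis shows how many events are affected.

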9.7.2 Main analysis

For the primary effectiveness outcomes incidence rates (events per 1,000patients-years) with corresponding 95% confidence intervals (CI) will be calculated. This will be evaluated by a matched Cox proportional hazards regression model for counting processes, which allow the follow-up time to be divided into several periods and therefore control for baseline and time-dependent covariates, using the full observational period of available data, i.e. up to 11 years of follow up. The Cox proportional hazards regression will take into account the fact that individual matching (1:1) will be performed by considering the exposed patient and his/her matched controls as one stratum and including this as a stratum in the Cox proportional hazards model. Additional variables will be included in the model if available. The cumulative incidence plots will be accompanied by number of patients at risk at different time points during follow-up. For (possibly) repeating events (such as exacerbation event) additionally a Poisson regression model will be fitted for the number of events (taking into account the matching). Time in the study will be included as an offset variable in the model. The cox and Poisson models will be adjusted for unbalanced PS-variables at baseline.

The outcome will be analyzed separately for each:

- 1) Primary outcome
 - Comparison of pneumonia incidence in COPD patients using LAMA and ICS/LABA
 - Comparison of exacerbations frequency and rate in COPD patients using LAMA and ICS/LABA : moderate or severe exacerbation

Proprietary confidential information © 2022 Boehringer Ingelheim International GmbH or one or more of its affiliated companies

[figure not shown]
- Comparison of time to start triple combination therapy (time from initial 'LAMA mono' or ICS+LABA' to 'LAMA+LABA+ICS' combination) in COPD patients using LAMA and ICS/LABA

2) Secondary outcome

- Comparison of all-cause mortality differences in COPD patients using LAMA and ICS/LABA
- Comparison of lung cancer incidence in COPD patients using LAMA and ICS/LABA
- Comparison of health care utilization: Medical cost / No. of prescriptions, visits and hospitalizations (hospitalization mainly due to severe exacerbation of COPD)

Health care utilization

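### The primary exacerbation endpoint is defined by the qualifying contact with no visible rule for grouping contacts into episodes, so a literal count inflates the annual rates in both arms

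*Combined protocol and SAP*

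**What the plan says.** The second primary endpoint in Section 9.3.2.1 is "Frequency rate of COPD exacerbation per year". It has two grades:

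- Moderate: "Moderate exacerbation: recorded as when COPD patients visited outpatient clinics with an ICD-10 code of COPD and systemic steroid medication and/or antibiotics were prescribed".
- Severe: "Severe exacerbation: when COPD patients visited the emergency room or were admitted to hospital with an ICD-10 code of COPD", with a qualifier that the contact was for worsening COPD and with the same prescription condition.

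Section 9.7.2 analyses both grades under one item: "Comparison of exacerbations frequency and rate in COPD patients using LAMA and ICS/LABA : moderate or severe exacerbation". Cox regression is the main model. For events that can repeat, "a Poisson regression model will be fitted for the number of events" in addition, and "Time in the study will be included as an offset variable in the model".

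The visible text gives no minimum gap between events and no episode window. It has no rule joining an outpatient visit to a later ER visit or admission, and no precedence of severe over moderate. Section 9.3 defers detailed variable definitions to a SAP, whose text is not among the documents. Annex 1 lists no stand-alone documents.

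**The concern.** An exacerbation is an episode, while a claims database records contacts. The definition says which contact qualifies and stops there. Suppose a patient is seen on day 1 with an antibiotic, reviewed on day 6 with a second course, and admitted on day 8. Taken literally, that is two moderate events and one severe event for a single exacerbation. A patient who collects a maintenance oral steroid or long-term antibiotic at monthly COPD visits could score about 12 events a year.

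Three results are exposed:

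- **Annual rates.** They would measure treated contacts and come close to the visit and hospitalization counts that Section 9.3.2.2 already lists as a separate secondary outcome.
- **Precision.** Contacts from one episode are not independent, so a plain Poisson variance is too small.
- **Rate ratio.** It moves if the number of contacts per episode differs between arms.

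Two analysts could follow the definition faithfully and obtain different counts for a primary endpoint.

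**Working it through.** **Inputs from the documents.** The unit of the definition is the contact (9.3.2.1). The outcome is the number of events with time as offset (9.7.2). Matching is 1:1 (9.7.1.1). The documents state no exacerbation rate, contacts per episode, effect size or power, so there is no figure of the plan to reproduce.

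**Assumption.** True episodes follow a Poisson distribution. Each episode yields K = 1 + Poisson(m) qualifying contacts, where m is the mean number of extra contacts. The values of m are mine.

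**Formulas.**

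- Counted rate = true rate × (1 + m).
- Variance-to-mean ratio D = E[K²]/E[K] = ((1 + m)² + m)/(1 + m).
- A correct confidence interval (log scale) is √D times as wide as the plain Poisson one.
- Type I error of a plain Poisson test at nominal 5% = 2 × (1 − Φ(1.96/√D)).

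| Contacts per episode, 1 + m | Rate too high by | D | √D | Type I error |
|---|---|---|---|---|
| 1.1 | 10% | 1.19 | 1.09 | 7.3% |
| 1.2 | 20% | 1.37 | 1.17 | 9.4% |
| 1.3 | 30% | 1.53 | 1.24 | 11.3% |
| 1.5 | 50% | 1.83 | 1.35 | 14.8% |
| 2.0 | 100% | 2.50 | 1.58 | 21.5% |

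A true rate of 1.0 per year would thus be counted as 1.1 to 2.0.

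**Rate ratio.** When the true ratio is 1.00, the reported ratio is (1 + m₁)/(1 + m₀):

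- Equal contacts per episode: 1.00, no bias.
- 1.3 against 1.2: 1.3/1.2 = 1.08. Reversed: 1.2/1.3 = 0.92.
- 1.5 against 1.3: 1.5/1.3 = 1.15. Reversed: 1.3/1.5 = 0.87.

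**Continuous supply.** If a share p of an arm refills monthly at COPD-coded outpatient visits, that arm gains 12p events per person-year. With an assumed p of 5%, this is 0.05 × 12 = 0.6. It becomes a difference between arms only to the extent that p differs between them.

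**Time to first event.** Merging dates an episode at its earliest qualifying contact, so the first event keeps its date. Only two things can move it: dropping claims that merely continue a supply, and regrading an episode if moderate and severe are analysed separately.

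**The case against.** A reader might infer that the plan orders every qualifying visit to be counted, so that the primary rate is known to be wrong. The documents do not support that. Section 9.3.2.1 says how an exacerbation is recognised in claims; it is silent on merging and does not rule it out. Detailed definitions are left to a SAP, and an episode gap is the kind of detail a SAP would hold. Annex 2 also cites a Section 9.7.3 for outcome validity, misclassification and sensitivity analyses, and that section is not in the public text.

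A reader might equally infer that the treatment comparison is biased. This too goes beyond the documents. With equal contacts per episode the ratio is unbiased. Asthma history, exacerbation history and the Charlson index are in the propensity score (9.7.1.1), and covariates with a standardised difference above 0.1 after matching are adjusted for. The cohort is meant to be inhaler-naive and the exacerbation definitions cover the first year, which makes established maintenance steroid or antibiotic use less obvious. Poisson regression is additional to Cox regression, and the planned allowance for matching might be implemented with a variance that also absorbs clustering.

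Most of this stands, and it limits the point to a missing counting rule with conditional consequences. It does not remove the point. A general deferral supplies no rule. Section 9.7 itself says that major changes to primary endpoint definitions belong in a protocol amendment, and the two amendments logged in Section 5 concern milestones only. Balance on recorded baseline covariates does not guarantee equal contacts per episode, and Section 9.9.4 accepts residual confounding. No overdispersion correction is named.

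**Conclusion.** The point holds as a gap in the definition of a primary endpoint. If the definition is applied literally, one exacerbation with a revisit or escalation is counted more than once, and absolute annual rates are inflated in both arms. The size cannot be derived from the documents: 10% to 100% corresponds to an assumed 1.1 to 2.0 contacts per episode. Under the same assumption, with contacts distributed as above, a plain Poisson test at nominal 5% has a type I error of 7.3% to 21.5% even when the arms do not differ in contacts per episode.

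Bias in the rate ratio is conditional on a difference between arms that remains after matching, and its direction is unknown (1.15 or 0.87 in the illustration). A Cox analysis of time to first exacerbation is largely unaffected. Whether unseen text already contains an episode rule cannot be determined.

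**What to change.** Add an episode rule to Section 9.3.2.1, and carry it into the SAP before the data are analysed:

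- Qualifying outpatient, ER and inpatient claims that start within a prespecified gap of the previous qualifying claim or discharge form one exacerbation. A gap of 14 days is an example; the documents do not fix a value.
- The exacerbation is dated at its earliest qualifying contact and graded by the most severe setting reached.
- Claims that only continue an uninterrupted steroid or antibiotic supply are not counted.
- The analysis is repeated with a longer gap, for example 28 days.
- The count model uses a robust or negative binomial variance.

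No new data are needed. Appendix Table 1 already lists treatment dates, first inpatient date, days of visit or stay, and days of medication. The cost is a short amendment and the programming, including a days-supply algorithm with its own rules for small breaks in supply and for inpatient drugs. The downside is that true exacerbations closer together than the gap are merged and the reported rates fall; the second gap length shows how much this matters.

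### The moderate exacerbation definition does not require a new acute course, so refills of long-term oral steroids or antibiotics at COPD-coded visits enter a primary event rate

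*Combined protocol and SAP*

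**What the plan says.** Section 9.3.2.1 lists "Frequency rate of COPD exacerbation per year" as a primary endpoint, with two components.

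- **Moderate:** COPD patients "visited outpatient clinics with an ICD-10 code of COPD and systemic steroid medication and/or antibiotics were prescribed", counted "within the first year after initial prescription of inhalers".
- **Severe:** an emergency room visit, or patients "admitted to hospital with an ICD-10 code of COPD(*due to COPD worsening*) and were prescribed systemic steroid medication and/or antibiotics", over the same window.

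Only the severe component carries a worsening qualifier. The moderate component has no condition on symptoms, new start, course length or gap between events.

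Among the drug-history exclusions in section 9.2 is "Prescription history with Leukotriene receptor antagonist(LTRA) or ICS". The others cover long-acting bronchodilators, ipratropium and LABA/LAMA combinations. IPF, ILD, lung cancer and lung transplantation at COPD diagnosis are also excluded. Long-term oral steroid or antibiotic use is not on the list.

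For repeating events, section 9.7.2 states that "additionally a Poisson regression model will be fitted for the number of events (taking into account the matching"), with time in study as offset. It gives no rule for deciding which visits form an event.

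The propensity list in section 9.7.1.1 has age and sex, socioeconomic status, exacerbation history, Charlson index and asthma history. Section 9.12 describes a wider score that also covers prior and concomitant use of other drugs.

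**The concern.** A patient on maintenance oral steroids or a long-term antibiotic may be given a refill at a routine COPD-coded visit. Under the moderate definition that refill is an exacerbation. Because the endpoint is a count per year, one such patient can contribute many events.

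This differs from counting one episode twice. Refills a month or more apart would pass an ordinary episode-gap rule and still be counted.

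If long-term use is more frequent in one arm, the rate ratio is biased by the difference. If it is equally frequent, the same number of false events is added to both rates and the ratio moves toward 1. Matching can only balance use that is present at baseline and represented in the score. It cannot correct for use that begins during follow-up.

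**Working it through.** The plan has no figure to reproduce. Section 9.5 gives a minimum of 5,000 patients per arm, with no event rate, effect size or power. The check is therefore a reading of the definition plus an illustration on declared assumptions.

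**Inputs, all assumed:** true rate r = 0.8 exacerbations per patient-year; share p of patients on long-term steroid or antibiotic, taken as what remains after matching; k = 6 to 12 COPD-coded refill visits a year per such patient.

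**Event-rate scale.** Recorded rate = r + p × k. With the same true rate in both arms (true ratio 1):

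| Use, ICS/LABA v LAMA | k | ICS/LABA rate | LAMA rate | Recorded ratio |
|---|---|---|---|---|
| 2% v 1% | 6 | 0.8 + 0.12 = 0.92 | 0.8 + 0.06 = 0.86 | 1.07 |
| 2% v 1% | 12 | 0.8 + 0.24 = 1.04 | 0.8 + 0.12 = 0.92 | 1.13 |
| 3% v 1% | 6 | 0.8 + 0.18 = 0.98 | 0.86 | 1.14 |
| 3% v 1% | 12 | 0.8 + 0.36 = 1.16 | 0.92 | 1.26 |

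**Equal use.** With 1% in both arms and a true ratio of 0.80 (0.64 v 0.80):
- k = 6: (0.64 + 0.06)/(0.80 + 0.06) = 0.81
- k = 12: (0.64 + 0.12)/(0.80 + 0.12) = 0.83

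**First-event scale.** Suppose every long-term user has an event within the year and the rest follow a constant rate of 0.8. One-year risk = (1 − p)(1 − e^−0.8) + p, with 1 − e^−0.8 = 0.551.
- p = 1%: 0.555; p = 2%: 0.560; p = 3%: 0.564
- Risk ratios: about 1.01 (2% v 1%) and 1.02 (3% v 1%)
- Cumulative hazard is 0.8 − ln(1 − p), or 0.810, 0.820 and 0.830, with ratios 1.013 and 1.025. This only approximates the hazard ratio from the pair-stratified model.

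**Wider range.** Let r run from 0.3 to 1.0, p from 1% to 5% and k from 4 to 12.
- Equal use: a true ratio of 1.20 is recorded as anything from (0.36 + 0.60)/(0.30 + 0.60) = 1.07 to (1.20 + 0.04)/(1.00 + 0.04) = 1.19.
- A 2-point gap in use (3% v 1%, or 5% v 3%) with a true ratio of 1: from (1.00 + 0.20)/(1.00 + 0.12) = 1.07 to (0.30 + 0.36)/(0.30 + 0.12) = 1.57.

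The far ends combine a low true rate with frequent refills, and either high use or a threefold difference in use between arms. Nothing in the documents indicates that this combination occurs.

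**The case against.** The case against has several good parts.

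- **Scope.** The severe component needs an emergency visit or admission for worsening. A refill counts only at an outpatient visit that carries a COPD code and falls in the first year; one issued under another diagnosis does not. This stands, and it confines the point to the moderate component.
- **Eligibility.** The cohort is meant to be inhaler-naive, and the exclusions for ICS, LTRA, IPF, ILD and transplantation probably remove some long-term steroid users. This also stands, but it reduces the group without excluding it.
- **Matching.** Asthma and prior exacerbation are in the score, imbalanced score variables are adjusted for, and section 9.12 mentions other drug use. The mitigation is real but partial. The operative list in section 9.7.1.1 has no drug-use term, so the two sections need reconciling.
- **Analysis.** Cox regression is planned for all outcomes and Poisson is additional, so a first-event reading leaves almost no effect. This is right for a first-event analysis. However, section 9.7.2 refers to a counting-process Cox model without saying whether repeat events enter, and the endpoint itself is an annual rate.
- **Text not seen.** Section 9.3 defers detailed definitions to a SAP, and a section after 9.7.2 is blacked out. A sensitivity definition may exist there, but it would not alter the primary definition in 9.3.2.1.

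A reader might infer that the whole exacerbation endpoint is invalid, or that it is known to be biased against ICS/LABA. The documents support neither. They give no prevalence of long-term use in either arm. Section 8 lists tuberculosis recurrence and non-tuberculous mycobacterial disease as expected events after long-term ICS, but says nothing about how often antibiotics for these would be prescribed at COPD-coded visits.

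**Conclusion.** The point holds for the moderate component. Applied as written, the rule counts maintenance refills at COPD-coded outpatient visits as primary events, and they accumulate in the Poisson rate.

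The size is unknown. With a true rate of 0.8 a year, 6 to 12 refill visits, and 2% against 1% use remaining after matching, the rate ratio would be falsely 1.07 to 1.13. The effect on a first-event Cox analysis would be about 1% to 2%, and attenuation would be slight at 1% use in both arms. The material risk is therefore unequal use in the event-rate analysis. The direction cannot be stated from the documents. Because this is a primary endpoint and the remedy is cheap, it should be corrected before analysis.

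**What to change.** 1. In section 9.3.2.1, do not count an outpatient prescription that continues ongoing supply of a systemic steroid or of the same antibiotic. One workable rule is that earlier supply covers most of the preceding 30 days. A new short course after an earlier completed short course would then still count, so genuine early relapses are kept.
2. Pre-specify in the SAP a maximum days-of-supply for an acute course. The supply rule catches refills; the length limit catches the first long prescription.
3. Add baseline long-term systemic steroid and antibiotic use to the propensity list in section 9.7.1.1, which also brings it closer to section 9.12.
4. Report the unrestricted definition as a sensitivity analysis.

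**Cost.** A protocol amendment would be expected, since section 9.7 says major changes to primary endpoint definitions are reflected in one. SAP text and a programming rule are also needed, but no new data. Some true exacerbations in long-term users will be missed. The prescription-level field in Appendix Table 1 is labelled "Total days of medication or frequency of medication", which is ambiguous between days and frequency, so it must be checked before use. The claim-level prescription-days field (TOT_PRES_DD_CNT) could serve as a cross-check.
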